10.5 Treatment Discontinuation

All subjects who discontinue due to an AE must be followed until the event resolves or stabilizes. Appropriate medical care should be provided until signs and symptoms have abated, stabilized, or until abnormal laboratory findings have returned to acceptable or pre-study limits. The final status of the AE will be reported in the subject's medical records and the appropriate eCRF.

Reasons for treatment discontinuation should be classified as follows:

- Death
- Progressive disease
- Treatment-related toxicity
- Toxicity unrelated to treatment
- Investigator judgment
- The Investigator may withdraw a subject if, in his/her judgment, it is in the subject's best interest to do so.
- Noncompliance
- Subject voluntary withdrawal
 - A subject may withdraw from the study at any time, for any reason. If a subject discontinues treatment, an attempt should be made to obtain information regarding the reason for withdrawal.
- Early withdrawal of subject(s)
- Sponsor decision

Subjects who are unavailable for follow-up evaluations should be classified as lost to follow-up for 1 of the following reasons:

- Lost to follow-up: For a subject to be considered lost to follow-up, the investigator must make two attempts to re-establish contact with the subject. The attempts to re-establish subject contact must be documented (e.g., certified letter).
- Death: Date and cause of death will be recorded for those subjects who die within 30 days after treatment (telephone contact is acceptable).

11.0 Procedures Involved

11.1 Participant Registration

Eligibility of each participant will be established prior to enrollment. Patients at Roswell Park will be registered directly by Roswell staff using the web-based registration system.

Informed consent MUST be completed prior to receiving any study related procedures.

11.2 Baseline Evaluations

The following will be performed within 8 weeks prior to administration of porfimer sodium:

- Informed consent: Must be completed prior to receiving any study-related procedures
- Medical history
- Physical examination including vital signs (i.e., temperature, heart rate, respiratory rate, blood pressure, body weight, height, and pain assessment using a verbal score of 0 10) *
- Hematology (i.e., complete blood count (CBC) with auto differential, absolute neutrophil count (ANC), and platelets) *, **
- Chemistry (i.e., AST, ALT, total bilirubin, alkaline phosphatase, creatinine, potassium, glucose, and calcium) *
- Pregnancy test (urine) in females of childbearing potential **
- ECOG Performance Status **
- UW OoLO v4 #
- Standard imaging for patients with HNC (i.e., CT and/or MRI) *, at least 10 business days prior to the scheduled I-PDT #
- Pretreatment planning #
- Concomitant Medications (including narcotic and nonnarcotic analgesics) **

**These will be done prior to later 2nd and 3rd later I-PDT sessions (if later I-PDT sessions are required per treating physician's discretion per Section 10.4). Height does not need to be reassessed for later possible I-PDT sessions. If later I-PDT courses are deemed necessary, previous study treatment adverse events will be reviewed before the start of next I-PDT course.

Performed as per PI discretion if 2nd and 3rd I-PDT courses are deemed necessary as per Section 10.4.

^{*}These are standard of care and may be used for baseline evaluation if performed before informed consent but within 4 weeks of porfimer sodium and can be used for the pretreatment planning.

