11.4 Evaluations Performed on the Day of Each I-PDT Treatment

- ECOG Performance Status
- Concomitant medication (including narcotic and nonnarcotic analgesics)
- Adverse events
- Pre-laser light research bloods (Optional) #
- Intraoperative ultrasound #
- Light dosimetry measurements

Performed per PI discretion if later I-PDT courses are deemed necessary as per Section 10.4.

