19.5 Quality-of-Life Analysis

UW-QoLQ v4 will be calculated at baseline and at 30 days post final treatment. The primary analysis will consist of examining the change from baseline to Day 30 using a Wilcoxon sign-rank test.

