Appendix D Schedule of Procedures and Observations if Only I-PDT Course is Necessary

Evaluation	Baseline ¹	Pre- Operative	Day of Treatment	Day 1 Post Treatment	1-week Post- treatment	Optional I-PDT Course 2 Within 2-3 Weeks of Day 0 ¹⁷	Clinic Visit ^{2,2a}	30- Day Post I- PDT ¹⁴	Optional I-PDT Treatment additional 2 or 3 At least 6 Weeks after last I-PDT Session ¹⁸	Follow- Up
Informed Consent	X									
Medical History	X								X	
Physical Exam/ Vital signs & pain assessment using a verbal score 0-10 ³	X				X		X	X	X	X
Hematology ⁴ and Chemistry ⁵	X				X		X	X	X	
Research Blood Draws ⁶			X		X		X	X	X	
Pregnancy Test (Urine)	X								X	
ECOG Performance Status	X		X		X		X	X	X	X
UW-QoLQ v. 4 ¹⁵	X				X		X	X	X	X
Standard Imaging of the head and neck with CT or MRI, for RECIST v11.1	X ⁷								X	X8
Treatment planning	X								X	
Porfimer Sodium administration and Vital Signs		X ⁹							X	
Intraoperative Ultrasound			X						X	
If possible, intraoperative CT or other clinically approved radiological imaging			X^{10}			X ¹⁰			X^{10}	
Interstitial PDT (I-PDT) 16			X^{11}			X ¹¹			X ¹¹	
Concomitant Medications	X ¹²		X							
Adverse Events ¹³			X		X		X	X		

Notes:

- * The I-PDT procedure is termed a "course".
 - 1. Performed within 8 weeks prior to porfimer sodium.
 - Performed at Day 1 of SOC therapy.
 If later 2nd and 3rd I-PDT courses are deemed necessary per the physician (see Section 10.4), please refer to Appendix D 1 for treatment, procedure, and test scheduling.
 - 3. Temperature, heart rate, respiratory rate, blood pressure, body weight and, height, Height collected at baseline only. Refer to Section 11.2.
 - 4. Hematology (i.e., CBC (with auto differential), ANC, and platelets). Refer to Section 11.2.
 - 5. Chemistry (i.e., AST, ALT, total bilirubin, alkaline phosphatase, creatinine, potassium, glucose, and calcium). Refer to Section 11.2.
 - 6. This is optional. Refer to immune markers Section 11.8 (1, 10 mL green-top tube).
 - 7. Standard tumor staging performed within 4 weeks, and at least 14 business days prior to I-PDT. If possible, the imaging will include temporary fiducial markers that will be affixed to skin. Refer to Section 11.2.
 - 8. CT scans at 10 to 12 weeks post SOC therapy and as clinically indicated following the NCNN 2018 guidelines.
 - 9. Infusion will occur 48 hours ± 8 h prior to illumination. Vitals are to be taken immediately after injection and after 15 minutes.

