Fresh Tissue Tumor Biopsy ^F	X			X			
Standard Imaging of the head and neck with CT or MRI ^G	XH						XI
Treatment planning	X						
Porfimer Sodium administration and Vital Signs		X^{J}					
Intraoperative Ultrasound ^Q			X				
If possible, intraoperative CT or other clinically approved radiological imaging			X ^K				
Interstitial PDT (I-PDT)			$X^{L, Li}$				
Concomitant Medications	X ^M		X				
Standard of care (SoC) chemotherapy, targeted therapy or potentially immunotherapy as first line palliative care treatment options					X ^N		
Adverse Events ^O	X ^{Oi}		X	X	X	X	

Notes:

^{*} The I-PDT procedure is termed a "course". As per later Section 10.4, study participants may have up to 3 I-PDT courses per physician's discretion, at least 30 days from the previous illumination procedure.

- ** NOTE: 2nd and 3rd I-PDT courses are per the physician's discretion as per Section 10.4, 2nd and 3rd I-PDT courses are not required for all study participants. If it is decided participants should receive all 3 I-PDT courses, items from "Repeat of Initial Tests and Procedures" until the completion of I-week Post treatment" are completed twice before the Clinic Visit and start of Standard of Care chemotherapy.
 - A. Performed within 4 weeks prior to 2nd and 3rd I-PDT courses. Since there may be up to three I-PDT courses, at least 30 days apart (see Section 10.4) per the physician's discretion, the initial procedures, exams, or tests may be completed up to two more times based on the individual participant's study treatment regimen. Research blood draws, standard imaging of head and neck with CT or MRI, and treatment planning for later I-PDT courses are per physician's discretion.
 - B. Temperature, heart rate, respiratory rate, blood pressure, and body weight. Refer to Section 11.2.
 - C. Hematology (i.e., CBC (with auto differential), ANC, and platelets). Refer to Section 11.2.
 - D. Chemistry (i.e., AST, ALT, total bilirubin, alkaline phosphatase, creatinine, potassium, glucose, and calcium). Refer to Section 11.2.
 - E. This is optional. Research blood draws for any 2nd and 3rd I-PDT courses (all timepoints) are per the physician's discretion. Refer to immune markers Section 11.8 (1 green top tube).

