Appendix E University of Washington Quality of Life Questionnaire

	Date:/ Subject ID#
	is questionnaire asks about your health and quality of life over the past seven days. Please wer all of the questions by checking one box for each question.
1.	Pain (Check one box:)
	I have no pain.
	There is mild pain not needing medication.
	I have moderate pain - requires regular medication (codeine or nonnarcotic).
	I have severe pain controlled only by narcotics.
	I have severe pain, not controlled by medication.
2.	Appearance (Check one box:)
	There is no change in my appearance.
	The change in my appearance is minor.
	My appearance bothers me but I remain active.
	I feel significantly disfigured and limit my activities due to my appearance.
	I cannot be with people due to my appearance.
3.	Activity (Check one box:)
	I am as active as I have ever been.
	There are times when I can't keep up my old pace, but not often.
	I am often tired and have slowed down my activities although I still get out.
	I don't go out because I don't have the strength.
	I am usually in bed or chair and don't leave home.
4.	Recreation (Check one box:)
	There are no limitations to recreation at home or away from home.
	There are a few things I can't do but I still get out and enjoy life.
	There are many times when I wish I could get out more, but I'm not up to it.
	There are severe limitations to what I can do, mostly I stay at home & watch TV.

Roswell Park Protocol No.: I 67918

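### The quality-of-life baseline may be up to 8 weeks old when porfimer sodium is given, so the baseline-to-Day-30 test mixes avoidable pre-drug change with change after I-PDT (minor)

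*Combined protocol and SAP*

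**What the plan says.** - **Window.** The UW-QoLQ v4 is in the Section 11.2 list headed "The following will be performed within 8 weeks prior to administration of porfimer sodium". Note 1 to the Baseline column of Appendix D agrees: "Performed within 8 weeks prior to porfimer sodium".
- **Marks on the item.** In Section 11.2 the form carries only the # mark: "Performed as per PI discretion if 2nd and 3rd I-PDT courses are deemed necessary as per Section 10.4". The shorter 4-week limit there belongs to the items with a single asterisk ("These are standard of care and may be used for baseline evaluation if performed before informed consent but within 4 weeks of porfimer sodium"), and the form is not one of them.
- **Between baseline and first light.** Section 11.3 (injection day) lists the injection and vital signs. Section 11.4 (day of I-PDT) lists ECOG status, concomitant medication, adverse events, optional bloods, ultrasound and dosimetry. Neither includes the questionnaire. Its row in Appendix D has no mark under Pre-Operative or Day of Treatment; the next score is 1 week after treatment.
- **Later courses.** Appendix D 1 marks the form again among items "Performed within 4 weeks prior to 2nd and 3rd I-PDT courses". Those scores come after the first I-PDT.
- **Analysis.** Section 19.5: "The primary analysis will consist of examining the change from baseline to Day 30 using a Wilcoxon sign-rank test". The later score is the one taken 30 days after final treatment. Section 9.0 gives I-PDT to all participants, so there is no control.
- **Recall.** The Appendix E form "questionnaire asks about your health and quality of life over the past seven days".
- **A different limit elsewhere.** Section 16.4 asks that all baseline evaluations be close to the start of treatment and at most 4 weeks before it, under a heading about evaluating measurable disease.

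**The concern.** A before-and-after comparison is only as good as its before value. Because the form recalls seven days, a permitted baseline can describe a week about two months before any drug or light. Participants have disease that failed standard therapy, and Section 2.1 says their quality of life is severely affected by local recurrence, so change during the wait is plausible. ECOG status and analgesic use are recorded again on the day of I-PDT; quality of life is not.

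With no control arm, any change during the wait enters the tested difference. A decline would make I-PDT look worse or hide a benefit. The contribution also varies between participants, since the wait can be anything from 0 to 56 days. Section 2.6.1 gives the purpose of the measurement as the unevaluated impact of Photofrin I-PDT on quality of life, and this is the only hypothesis test planned for it.

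**Working it through.** **The plan's own figure.** The plan states no power, SD, alpha or effect size for this test. The only design figure is the maximum sample size: 4 cohorts × 3 = 12 (Sections 4.0 and 19.1), which reproduces.

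**Inputs.** Baseline up to 8 weeks = 56 days before drug (11.2, Appendix D note 1); drug to light 48 ± 8 hours, taken as 2 days (11.3); final score 30 days after final treatment (19.5); up to three courses at least 30 days apart (10.4).

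**Length of the tested interval.** Days = baseline gap + 2 + 30 × (courses − 1) + 30.

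| Baseline gap | Courses | Total days | Before drug | Before first light |
|---|---|---|---|---|
| 56 | 1 | 56 + 2 + 30 = 88 | 56 (64%) | 58 (66%) |
| 56 | 3 | 56 + 2 + 60 + 30 = 148 | 56 (38%) | 58 (39%) |
| 28 (if 16.4 governed) | 1 | 28 + 2 + 30 = 60 | 28 (47%) | 30 (50%) |
| 0 (injection day) | 1 | 0 + 2 + 30 = 32 | 0 | 2 (6%) |

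**Effect on the test (illustration).** Assumptions not in the documents: two-sided alpha 0.05, normally distributed change scores, true I-PDT effect zero, every participant at the 8-week limit, and drift only before the drug. Drift is in SDs of the paired change per 8 weeks. The exact signed-rank test has size 2/2⁶ = 3.1% at n=6 and 174/4096 = 4.2% at n=12. Rejection rates from 100,000 simulated trials:

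| Pre-drug drift | n=12 | n=6 |
|---|---|---|
| 0.25 SD | 10.8% | 5.0% |
| 0.5 SD | 31.5% | 10.8% |

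**Sensitivity to the gap** (n=12, 0.5 SD per 8 weeks): a 28-day baseline gives 10.7%, a 7-day baseline 4.6%, and a day-0 baseline 4.4%, which is the test size within simulation error. If gaps are spread uniformly over 0 to 56 days and drift reaches 0.5 SD at day 56, a separate run of 20,000 trials gives 10.7%.

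**What a fresh baseline does not remove.** Let the same 0.5 SD per 8 weeks run on to Day 30 (n=12, one course). The 56-day baseline then rejects in 65.3% of trials and the day-0 baseline in 12.8%. The pre-drug part goes; the untreated drift after the drug stays.

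**The case against.** Several points against the concern have force.

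- **Section 16.4.** Its 4-week sentence refers to all baseline evaluations without exception. If it governs the questionnaire, the gap is 28 days, and the 0.5 SD illustration falls from 31.5% to 10.7%. But it sits under measurable disease, and read broadly it contradicts the 8 weeks in Section 11.2 and Appendix D. Even then, 47% of the one-course interval precedes the drug.
- **Eight weeks is a maximum.** This stands. The documents give neither a distribution of gaps nor a rate of decline. A reader might infer that the trial's expected false-positive rate is around 31%; that does not follow. The figure needs 12 participants, all at the limit, with an assumed drift. Twelve is itself a maximum.
- **No causal claim in Section 19.5.** Also true. A reader might infer that the plan counts pre-treatment decline as an effect of I-PDT, but Section 19.5 only examines a change. The causal reading comes from the purpose in Section 2.6.1 together with the absence of a control.
- **The form is repeated.** It is marked before courses 2 and 3, so it would be wrong to say that it is never repeated before a treatment. Those repeats come too late to be a pre-treatment baseline.
- **Low consequence.** Quality of life is not among the Section 1 objectives or the Section 8 endpoints, and no dose, safety or stopping decision uses it. The ECOG and analgesic records on the day of I-PDT would show gross deterioration in part.

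**Conclusion.** The concern holds in a limited form. The schedule allows a quality-of-life baseline up to 56 days before the drug, with nothing closer before first light, so the Section 19.5 test mixes avoidable pre-drug change with change after I-PDT. The timeline follows directly from the documents: up to 58 of 88 days (66%) before light for one course, and 58 of 148 (39%) for three courses at minimum spacing.

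The size of the resulting bias is not established. The 11 to 31% (n=12) and 5 to 11% (n=6) rejection rates rest on the assumed drift, alpha and gap, and show sensitivity only. The bias could also run the other way if quality of life improves during the wait.

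A reader might also infer that a fresh baseline would turn this into a test of I-PDT. It would not: drift from drug to Day 30, and across repeat courses, remains in an uncontrolled comparison. Severity is minor, because the analysis is correlative and the primary safety objective is untouched.

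**What to change.** - Give the UW-QoLQ v4 on the day of the first porfimer sodium injection, before the injection. Its seven-day recall then covers the week just before the drug.
- Name that score as the baseline in Sections 19.5 and 2.6.1. Add it to Section 11.3 and to the Pre-Operative column of Appendix D.
- Keep the screening score only as a fallback when the injection-day score is missing, and report how many participants needed it and how old their scores were.
- State whether the 4-week sentence in Section 16.4 applies only to disease measurements, so that it no longer appears to conflict with the 8-week window.
- Add a sentence to Section 19.5 that the change is uncontrolled, includes drift from drug to Day 30 and across repeat courses, and cannot be attributed to I-PDT alone.

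The cost is a few minutes per participant at a visit that already takes place, plus the wording changes. One drawback is that a score taken about two days before a procedure may carry anticipatory anxiety, chiefly in the mood and anxiety items (11 and 12). Having the screening score as well lets this be looked at descriptively.

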11.3 Pre-operative - Day of Porfimer Sodium Injection

- 48 ± 8 hours before illumination
- Porfimer sodium solution (following the USPI) by a single slow intravenous injection over 3-5 minutes at 2 mg/kg body weight
- Vital signs will be done immediately after the end of the injection and 15 minutes later

11.4 Evaluations Performed on the Day of Each I-PDT Treatment

- ECOG Performance Status
- Concomitant medication (including narcotic and nonnarcotic analgesics)
- Adverse events
- Pre-laser light research bloods (Optional) #
- Intraoperative ultrasound #
- Light dosimetry measurements

Performed per PI discretion if later I-PDT courses are deemed necessary as per Section 10.4.

11.5 Evaluations Performed at 1st Post-Operative Clinic Visit

This visit will be scheduled 1 to 4 weeks post I-PDT and will include:

- Physical examination, including vital signs (i.e., temperature, heart rate, respiratory rate, blood pressure, body weight, and pain assessment using a verbal score of 0-10)
- Hematology (i.e., CBC (with auto differential), ANC, and platelets)
- Chemistry (i.e., AST, ALT, total bilirubin, alkaline phosphatase, creatinine, potassium, glucose, and calcium)
- ECOG Performance Status
- Adverse events
- UW QoLQ v4
- Research blood draws (Optional) #

Performed as per PI discretion if later I-PDT courses are deemed necessary as per Section 10.4.

11.6 Post-Treatment Follow-Up

Follow-up safety evaluations will occur every 1-3 months during the first year and then every 2-6 months in the second year after I-PDT day.

Follow-up Clinic Visits

Participants will be followed according to the 2018-NCCN follow-up guidelines for patients with advanced HNC(63). The study related visits occur up to 2 years, thus every 1-3 months in the first year, and every 2-6 months in the second year. The efficacy will be determined at 10-12 weeks after the initial study related treatment (see Section 8.1).

13MAR2023; SRC 18SEP2023; IRB 15NOV2023

If it turns out that a participant will be scheduled to have a routine visit at 10-12 weeks (which is within 1-3 months), we will not schedule another study visit. We will use the routine visit (at 10-12 weeks) to record data for the study. The routine clinical follow up will be up to 5 years.

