8.0 Study Endpoints

8.1 Primary Endpoints

Phase 1:

o The safety will be determined by recording the occurrence of AE during the first 30 days post final I-PDT day, using the revised NCI Common Terminology Criteria for Adverse Events (CTCAE) version 5.0.

Exploratory Endpoint

Objective target tumor response rates will be assessed according to RECIST v1.1 at 12 ± 2 weeks post I-PDT as described in section 16.2.

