9.0 Study Design

All participants will meet the inclusion and exclusion criteria summarized in Section 3.1 and Section 3.2 prior to taking part in this study.

This study will recruit subjects with HNC who failed to respond to standard therapy and are not candidates for salvage surgery or radiation therapy including re-irradiation. These HNC subjects would otherwise receive SoC chemotherapy, targeted therapy or potentially immunotherapy as first line palliative care treatment options.

All participants will receive I-PDT. All participants will have a standard diagnostic head and neck scan with CT or MRI, with or without contrast. Participants will be followed according to the 2018-NCCN follow-up guidelines (63; Appendix H) for patients with advanced HNC (https://www.nccn.org/professionals/physician_gls/pdf/head-and-neck.pdf). The study related visits would be up to 2 years, thus every 1-3 months in the first year, and every 2-6 months in the second year. The routine clinical follow up will be up to 5 years. The study schema is shown in

[figure not shown]
[figure not shown]

Figure 3 Study Schema

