16.2 Target Lesions

The target lesions will be the locally advanced HNC that were treated with I-PDT or the ones that were identified by the principal investigator (or treating physician) as locally advanced and were treated with SoC therapy. Tumors measurements will take place 10-12 weeks after I-PDT or the first SoC in the control ram. Change in the target tumor size will be determine using the methods described in RECIST v1.1 (62). CT with contrast or MRI (when CT is not possible) will be used to determine change in tumor size. The objective response of the target tumor will be determined following these criteria:

- Complete Response (CR): Disappearance of all target lesions. Any lymph nodes must have a reduction in short axis to < 10 mm.
- Partial Response (PR): At least a 30% decrease in the sum of diameters of target lesions, taking as reference the baseline sum diameters. A biopsy will be taken from the suspected lesions for histological confirmation.
- **Progressive Disease (PD):** At least a 20% increase in the diameters of target lesions, taking as references the smallest sum on study (this includes the baseline sum if that is the smallest on study). In addition to the relative increase of 20%, the sum must also demonstrate an absolute increase of at least 5 mm.

• **Stable Disease (SD):** Neither, sufficient shrinkage to qualify for PR nor, sufficient increase to qualify for PD, taking as reference the smallest sum diameters while on study, the response will be listed with stable disease. In this case, a biopsy will be taken from the suspected lesion for histological confirmation.

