19.4 Exploratory

Objective tumor response rates at 10-12 weeks will be summarized with a sample proportion and corresponding 95% confidence interval. Time-to-event endpoints will be examined using a Cox regression model with a factors for I-PDT (yes/no), standard-of-care type (chemotherapy, targeted therapy, immunotherapy) and an interaction term. Survival curves will be estimated per group using Kaplan-Meier estimates. It is assumed a priori that any drop out times will be non-informative in terms of the censoring mechanism.

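### The response scan has no single time zero: the schedule's SOC anchor can miss the endpoint window, and first versus last I-PDT is unsettled after repeat courses

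*Combined protocol and SAP*

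**What the plan says.** Section 1.2 lists one exploratory objective, the objective tumor response rate. Its scan is timed in six places:

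- Section 8.1, Exploratory Endpoint: "12 ± 2 weeks post I-PDT as described in section 16.2". It does not say which I-PDT.
- Section 16.2, to which 8.1 points: "Tumors measurements will take place 10-12 weeks after I-PDT or the first SoC in the control ram". There is no control arm; Section 9.0 states "All participants will receive I-PDT".
- Section 11.6, which cites 8.1: "The efficacy will be determined at 10-12 weeks after the initial study related treatment (see Section 8.1").
- Appendix D, which Section 11.7 names as the study schedule. The follow-up cell of the RECIST imaging row carries note 8: "CT scans at 10 to 12 weeks post SOC therapy and as clinically indicated following the NCNN 2018 guidelines". Note 14 foresees patients who receive no therapeutic SOC.
- Appendix D 1, note G: CT at 10-12 weeks post I-PDT.
- Section 19.4, the analysis text: "Objective tumor response rates at 10-12 weeks will be summarized with a sample proportion and corresponding 95% confidence interval". No time zero is given.

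Repeat treatment is allowed. Section 10.4 permits up to three I-PDT sessions at least 30 days apart, at the physician's discretion, and uses the date of the last course to schedule the follow-up SoC. For second and third courses Appendix D note 2a says "please refer to Appendix D 1 for treatment, procedure, and test scheduling"; the title of Appendix D 1 restricts it to later sessions, and its note N places Phase 1 patients in follow-up 30 days after the last I-PDT. Appendix D note 18 repeats all tests around an additional drug-and-light treatment, whereas Appendix D 1 note A leaves imaging for later courses to the physician. (The letters in Appendix D 1 do not line up with its table; notes are cited here by the letter printed beside the text.)

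**The concern.** Section 19.4 reports one proportion, so each patient must contribute one identifiable scan. The endpoint, follow-up, measurement, schedule and analysis sections do not define the same scan, and the cross-references do not settle it: 8.1 points to 16.2 and 11.6 points to 8.1, each to different timing.

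Sites work from the schedule. If they follow note 8, the scan can fall outside the endpoint window and after SOC has begun, so that a response may reflect SOC as well as I-PDT. After a repeat course, an early scan and a late scan could each be defended as the response scan. The reported rate could then mix patients scanned about three months after their only illumination, patients scanned a few weeks after a later course, and patients scanned on a clock started by SOC.

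**Working it through.** The plan offers no derived figure for response. Its one relevant number, the maximum sample size in Section 4.0, reproduces: 4 cohorts × 3 = 12. The rest is day counting, with day 0 = first illumination.

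**1. Windows.** 10-12 weeks = 10×7 to 12×7 = days 70-84. 12 ± 2 weeks = 10×7 to 14×7 = days 70-98.

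**2. One course, no SOC anchor.** Sections 11.6, 16.2 (I-PDT branch) and 8.1 all count from the same event, apart from the drug being given about 48 hours before light. Days 70-84 lie inside days 70-98. The windows are nested, not equal: a scan on days 85-98 meets 8.1 but not the 10-12 weeks of 19.4.

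**3. One course, note 8.** Note 8 does not say whether it counts from the start or the end of SOC, and no SOC start date is given. Assume it counts from a start on day S; the window is then S+70 to S+84.
- Misses days 70-84 when S+70 > 84, that is S > 14.
- Misses days 70-98 when S+70 > 98, that is S > 28.

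As an illustrative range, Appendix D note 2 puts the clinic visit on SOC day 1 and Section 11.5 puts the first post-operative visit 1-4 weeks after I-PDT. If these are the same visit, S is 7 to 28. S = 7 gives days 77-91, overlapping both windows. S = 15 gives days 85-99, outside 70-84. S = 28 gives days 98-112, sharing only day 98 with 8.1. For a patient without SOC, S does not exist and note 8 gives no date.

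**4. Repeat courses.** Let the last illumination be on day L. The 11.6 scan falls 70−L to 84−L days after it. If 8.1 is counted from the last illumination, its window is L+70 to L+98. Section 10.4's minimum spacing gives L = 30 for two courses and L = 60 for three.

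| L | 11.6 scan, days after L | 8.1 window counted from L | Overlap with days 70-84 |
|---|---|---|---|
| 0 | 70-84 | 70-98 | 70-84 |
| 30 | 40-54 | 100-128 | none (100−84 = 16 days apart) |
| 60 | 10-24 | 130-158 | none (130−84 = 46 days apart) |

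Overlap needs L+70 ≤ 84, that is L ≤ 14. If 8.1 is counted from the first I-PDT instead, 8.1 and 11.6 do not conflict.

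**5. Split and light-only sessions.** A session split within 14 days (note 16) has L ≤ 14, so the windows still meet, at the limit on day 84 alone. Light-only treatment under note 17 is 2-3 weeks after the drug, hence about days 12-19 after first light: windows 82-110 (sharing days 82-84) to 89-117 (5 days clear of day 84). The column heading reads "Optional I-PDT Course 2 Within 2-3 Weeks of Day 0"; if Day 0 is the light day, L is 14 to 21 and the windows run from 84-112 to 91-119. Either way the discrepancy is small, but neither kind of session has a stated time zero.

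**6. Number of scans.** Under note 18 a repeat-course patient has scans timed from both treatments. Under Appendix D 1 note A the second may never be taken. The two notes disagree, so the count of eligible scans is itself undetermined.

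**7. Scale.** With 12 patients, one reclassified patient moves the rate by 1/12 = 8.3 percentage points. For illustration, the exact 95% interval is 2.1% to 48.4% for 2/12 and 5.5% to 57.2% for 3/12.

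**The case against.** The strongest reply is that much of this is untidy wording. With a single course, a scan at 10-12 weeks meets every I-PDT-anchored passage. The control-arm branch of 16.2 applies to nobody. Section 8.1 can be read through 11.6 as meaning the initial treatment. Repeat courses are discretionary, and nothing says how many patients will have them. The endpoint is exploratory, carries no test, and its interval is wide whichever scan is used.

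Most of that stands, and it rules out stronger readings that a reader might infer:

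- That 8.1 and 11.6 contradict each other for every patient. They do not; with one course their windows are nested.
- That 11.6 is the only text choosing between courses. Section 10.4 and Appendix D 1 note N both work from the last course. They concern follow-up SoC and the start of follow-up rather than the response scan, so they do not settle the anchor, but they pull against 11.6.
- That every repeat-course patient will have two competing scans. That depends on notes 18 and A, which conflict.
- That routine CT every 1-3 months (Section 16.1) ensures a scan near any anchor. In Appendix H, which 16.1 cites, that interval is for history and physical examination; imaging is to be considered within 6 months or done as indicated.

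The reply does not dispose of note 8, which sits in the operative schedule, uses a clock that no endpoint text shares for treated patients, and fails without SOC. Nor does it settle first versus last I-PDT.

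**Conclusion.** The concern holds in a limited form and should be corrected before response is analysed. For one course, the substantive conflict is Appendix D note 8: counted from SOC start, it misses the 10-12 week window when SOC begins after day 14 and the 8.1 window when it begins after day 28. For repeat courses, the text does not say consistently whether the first or the last I-PDT sets the clock, and at 30-day spacing the two readings give windows that do not overlap.

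This rests on two assumptions: that note 8 counts from SOC start, and that courses follow the minimum spacing in Section 10.4. Longer spacing only widens the gap.

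A reader might infer that the response rate will be biased by a known amount or that the trial's main conclusion is at risk. The documents support neither. They do not give SOC start dates or the frequency of repeat courses, so no bias can be computed; the effect is confined to one descriptive proportion in at most 12 patients; and the Phase 2 light dose rests on DLT counts.

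**What to change.** - Delete the SOC anchor in Appendix D note 8 and the control-arm wording in Section 16.2.
- Put one window and one explicitly named time zero in Sections 8.1, 11.6, 16.2 and 19.4 and in Appendices D and D 1. The time zero is either the first or the last I-PDT illumination; the text compels neither, so this is the sponsor's choice, to be reconciled with Section 10.4 and Appendix D 1 note N. State how split and light-only sessions count.
- Reconcile Appendix D note 18 with Appendix D 1 note A, so that it is clear whether the scan is taken after a later course, and have 19.4 identify a single scan per patient.
- List patients who had a further illumination or started SOC before that scan.

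The cost is wording in six places and one listing. Each anchor has a drawback. Counting from the last illumination reads response later in repeat-course patients (day 100 at the earliest with a second course on day 30), when some may have started SOC or progressed. Counting from the first reads some patients soon after a later course. Under either choice a suitable scan may not already be planned for every patient, so a few additional scans may be needed.
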